353 the following order:

- 354 • % time <70 mg/dL
- 355 • % time <54 mg/dL
- 356 • Rate of hypoglycemic events

357 The process moves to the next variable down on the list until a non-significant result ($p \geq 0.025$)
358 is observed, or all outcomes have been tested. If a non-significant result is encountered, then
359 formal statistical hypothesis testing is terminated and any comparisons below on the list are not
360 formally tested. If for either comparison of interest, PLGS vs. SAP or HCL vs. SAP, all three
361 outcomes are rejected at the level of 0.025, the alpha can be recycled and the other comparison can
362 be tested down the hierarchy at an alpha level of 0.05 rather than 0.025.

363 See the next page for examples of possible scenarios.

364 **16.2. Other Secondary and Exploratory Analysis**

365 For all other secondary and exploratory outcomes, the false discovery rate will be controlled using
366 the Benjamini-Hochberg procedure method adapted using the two-stage test. For these analyses,

367 the adjusted p-value and 95% confidence interval will be reported. The categories for FDR
368 correction will be:

369 • HCL vs. SAP and PLGS vs. SAP

370 1. Glycemic control outcomes (overall, daytime, and nighttime CGM metrics and
371 HbA1c), CGM use, and insulin metrics

372 2. Patient-reported outcomes

373 3. Subgroups

374 • HCL vs. PLGS

375 4. Glycemic control outcomes (overall, daytime, and nighttime CGM metrics and
376 HbA1c), CGM use, and insulin metrics

377 5. Patient-reported outcomes

378 There will be no adjustment for safety outcomes.

379 *Example 1*

380 All tests for the PLGS vs. SAP comparison are significant, so we can recycle the alpha 0.025 and use it for the HCL vs. SAP
381 comparisons.

HIERARCHICAL ORDER	OUTCOME VARIABLE	HCL VS. SAP				PLGS VS. SAP			
		ALPHA	P-VALUE	SIGNIFICANT?	ACTION	ALPHA	P-VALUE	SIGNIFICANT?	ACTION
1 st	% time <70 mg/dL	0.05	0.04	Yes	Test next variable	0.025	0.001	Yes	Test next variable
2 nd	% time <54 mg/dL	0.05	0.06	No	Stop formal testing	0.025	0.02	Yes	Test next variable
3 rd	Rate of hypoglycemic events	0.05	Not tested	Unknown	N/A	0.025	0.007	Yes	Recycle alpha to HCL vs. SAP

382

383 *Example 2*

HIERARCHICAL ORDER	OUTCOME VARIABLE	HCL VS. SAP				PLGS VS. SAP			
		ALPHA	P-VALUE	SIGNIFICANT?	ACTION	ALPHA	P-VALUE	SIGNIFICANT?	ACTION
1 st	% time <70 mg/dL	0.025	0.04	No	Stop formal testing	0.025	0.001	Yes	Test next variable
2 nd	% time <54 mg/dL	0.025	Not tested	Unknown	N/A	0.025	0.02	Yes	Test next variable
3 rd	Rate of hypoglycemic events	0.025	Not tested	Unknown	N/A	0.025	0.07	No	Stop formal testing

384

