1148 determination and no later than 15 working days after first receipt notice of the UADE.

1149 Device malfunctions will be handled by the Coordinating Center.

1150 **9.4 Stopping Criteria**

1151 **9.4.1 Participant Discontinuation of Study Phase**

1152 Rules for discontinuing study device use are described below.

- 1154 • The investigator believes it is unsafe for the participant to continue on the intervention.
1155 This could be due to the development of a new medical condition or worsening of an
1156 existing condition; or participant behavior contrary to the indications for use of the device
1157 that imposes on the participant's safety
- 1158 • The participant requests that the treatment be stopped
- 1159 • Two distinct episodes of DKA (as defined in section 9.1.2) unrelated to infusion set
1160 failure
- 1161 • Greater than two distinct severe hypoglycemia events as defined in section 9.1.2.1
- 1162 • Participants who obtain a total score of 6 or less on the 5-min MoCA administered after
1163 an SAE occurrence.

1164 Even if the study device system is discontinued, the participant will be encouraged to remain in
1165 the study through the final study visit.

1166

1167 **9.4.2 Criteria for Suspending or Stopping Overall Study**

1168 In the case of an unanticipated system malfunction resulting in a severe hypoglycemia or severe
1169 hyperglycemia event (as defined in Section 9.1.1), use of the study device system will be
1170 suspended while the problem is diagnosed.

1171 In addition, study activities could be similarly suspended if the manufacturer of any constituent
1172 study device requires stoppage of device use for safety reasons (e.g. product recall). The
1173 affected study activities may resume if the underlying problem can be corrected by a protocol or
1174 system modification that will not invalidate the results obtained prior to suspension.

1175 The study Medical Monitor will review all adverse events and adverse device events that are
1176 reported during the study typically on a weekly basis and will review compiled safety data at
1177 periodic intervals (generally timed to the review of compiled safety data by the DSMB). The
1178 Medical Monitor may request suspension of study activities or stoppage of the study if deemed
1179 necessary based on the totality of safety data available.

1180 **9.5 Independent Safety Oversight**

1181 A Data and Safety Monitoring Board (DSMB) will be formed according to NIDDK requirements

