1390 treatment arm.

- 1391 • Number of adverse events
- 1392 • Number of serious adverse events
- 1393 • Number of unexpected device events
- 1394 • Number of SH events and SH incidence rate per 100 person-years
- 1395 • Number of hospitalizations related to a SH event
- 1396 • Number of ER visits related to a SH event
- 1397 • Number of fractures related to a SH event
- 1398 • Number of falls related to a SH event
- 1399 • Number of DKA events and DKA incidence rate per 100 person-years
- 1400 • Number of hospitalizations related to a DKA event or severe hyperglycemia
- 1401 • Number of ER visits related to a DKA event or severe hyperglycemia

1402 If there are enough events for statistical analysis, the SH and DKA incidence rates will be
1403 compared between treatment arms using a repeated measures Poisson regression model adjusting
1404 for period and whether the subject had an event in the 12 months prior to the study as a covariate.
1405 If there are zero events in one treatment arm, Poisson regression will not converge and so the
1406 number of events will be compared pairwise using Barnard's test instead.

1407 **11.9 Protocol Adherence and Retention**

1408 The following will be performed according to treatment arm:

- 1409 • A flow chart accounting for all participants for all visits
- 1410 • Tabulation of visit completion rates for each follow-up visit
- 1411 • Tabulation of protocol deviations

1412 • Tabulation of number and reasons for unscheduled visits and phone calls
1413 • Tabulation of device issues

1414 **11.10 Baseline Descriptive Statistics**

1415 Baseline demographic and clinical characteristics will be summarized in a table. For continuous
1416 variables, summary statistics appropriate to the distribution will be given. For discrete variables,
1417 number and percentage will be reported for each category.

1418 **11.11 Planned Interim Analyses**

1419 No formal interim efficacy analysis is planned for this study. Safety data tabulations will be
1420 performed at least every 6 months for review by the Data and Safety Monitoring Board (DSMB).

1421 **11.12 Sub-Group Analyses**

1422 Subgroup analyses/assessments of effect modification (interaction) will be conducted for the
1423 primary outcome. These analyses will be considered exploratory. Additionally, interpretation of
1424 the analyses will depend on whether the overall analysis demonstrates a significant treatment

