6 safety of both hybrid closed loop control (HCL) technology and predictive low-glucose insulin
7 suspension (PLGS) compared to sensor-augmented pump (SAP) therapy in older adults >65
8 years with type 1 diabetes. Eligible participants will receive all three interventions and the order
9 of receiving them will be randomized on a 1:1:1:1:1:1 ratio.

10 Randomization will be preceded by a run-in period where participants must demonstrate
11 competency and compliance in using the study insulin pump and CGM device. After
12 randomization, the subjects will enter the three 12 week study periods and will test one
13 intervention per study period.

14 **2. Comparison to Protocol**

15 The author of this SAP has verified that the analyses described in this document are consistent
16 with the version of the protocol listed in the version history table above except for the following:

- Removed tabulation of percent of time spent in sleep mode outside of nighttime hours
- Added tabulation of days per week of sleep mode use and exercise mode use

19 **3. Statistical Hypotheses**

20 A. *Null hypothesis*: There will be no difference in percentage of CGM-measured glucose
21 values <70 mg/dL between PLGS vs SAP.

22 *Alternate hypothesis*: There is a non-zero difference in the percentage of CGM-measured
23 glucose values <70 mg/dL between PLGS vs SAP.

24 B. *Null hypothesis*: There will be no difference in percentage of CGM-measured glucose
25 values <70 mg/dL between HCL vs. SAP.

26 *Alternate hypothesis*: There is a non-zero difference in the percentage of CGM-measured
27 glucose values <70 mg/dL between HCL vs. SAP.

28 **4. Sample Size**

29 Data from the CGM group in the WISDM randomized clinical trial of older adults ≥ 60 years of
30 age were used to estimate the standard deviation and frequency of time <70 mg/dL in the SAP
31 control period. Data from the two weeks prior to the 4 week visit were used to mimic the run-in
32 period in this study where the minimum hypoglycemia eligibility criteria will be assessed. Only
33 WISDM CGM group participants who had $\geq 2\%$ of time <70 mg/dL at the 4 week time point
34 were included. Data from the two weeks prior to the 26-week visit for these participants were
35 then used to estimate standard deviation and frequency of time <70 mg/dL. N=50 WISDM
36 participants were included of which 28 were injection users and 22 were pump users.

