227 “undetermined”. If the subject withdraws from the study in the middle of a period and the end of
228 treatment visit for that particular period does not occur, then the later of the last visit date, last
229 AE date or final status date (if known) will be used as the last day of the period for the purpose
230 of calculating event rates.

231 For the following outcomes, summary statistics appropriate to the distribution will be tabulated
232 by treatment arm.

- 233 • Number of adverse events
- 234 • Number of serious adverse events
- 235 • Number of unexpected device events
- 236 • Number of SH events and SH incidence rate per 100 person-years
- 237 • Number of hospitalizations related to a SH event
- 238 • Number of ER visits related to a SH event
- 239 • Number of fractures related to a SH event
- 240 • Number of falls related to a SH event
- 241 • Number of DKA events and DKA incidence rate per 100 person-years
- 242 • Number of hospitalizations related to a DKA event or severe hyperglycemia
- 243 • Number of ER visits related to a DKA event or severe hyperglycemia

244 If there are at least 5 SH events across treatment arms, the SH incidence rate will be compared
245 pairwise between all treatment arms using a repeated measures Poisson regression model
246 adjusting for period and whether the subject had an event in the 12 months prior to the study as a
247 covariate. If there are zero events in one treatment arm, Poisson regression will not converge and
248 so the number of events will be compared pairwise using Barnard's test instead. A similar
249 analysis will be done for DKA events if there are at least 5 events across the treatment arms.

250 **10. Protocol Adherence and Retention**

251 The following will be performed according to treatment arm:

- 252 • A flow chart accounting for all participants for all visits
- 253 • Tabulation of visit completion rates for each follow-up visit

254 • Tabulation of protocol deviations
255 • Tabulation of number and reasons for unscheduled visits and phone calls
256 • Tabulation of device issues

257 **11. Baseline Descriptive Statistics**

258 The following baseline demographic and clinical characteristics will be summarized in a table:

259 • Age
260 • Gender
261 • Race/ethnicity
262 • Income, education, employment, and/or insurance status
263 • Diabetes duration
264 • Age at diagnosis
265 • Insulin method before enrollment (pump vs. MDI)
266 • CGM use before enrollment
267 • AID use before enrollment

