268 • HbA1c
269 • BMI
270 • C-peptide
271 • Participant reported number of SH and DKA 12 months prior to the start of the study
272 • MoCA total score
273 • WAIS-IV Processing Speed Index
274 • FAQ score
275 • Frailty walk time
276 • Baseline CGM metrics including:
277 ○ % time <70 mg/dL
278 ○ % time <54 mg/dL
279 ○ % in range 70-180 mg/dL
280 ○ % time >180 mg/dL
281 ○ Coefficient of variation

282 For continuous variables, summary statistics appropriate to the distribution will be given. For
283 discrete variables, number and percentage will be reported for each category.

284 **12. Planned Interim Analyses**

285 No formal interim efficacy analysis is planned for this study. Safety data tabulations will be
286 performed at least every 6 months for review by the Data and Safety Monitoring Board (DSMB).

287 **13. Subgroup Analyses**

288 Subgroup analyses/assessments of effect modification (interaction) will be conducted for the
289 primary outcome. These analyses will be considered exploratory. Additionally, interpretation of
290 the analyses will depend on whether the overall analysis demonstrates a significant treatment
291 group difference; in the absence of such an overall difference, subgroup analyses will be
292 interpreted with caution. The general approach for these exploratory analyses will be to add an

293 interaction term for the subgroup factor by treatment into the models used for the primary
294 analyses.

295 The baseline factors listed below will be assessed:

296 • Race/Ethnicity
297 • Gender
298 • Baseline % time <70 mg/dL
299 • Age
300 • Education (\leq Bachelor's vs. >Bachelor's)
301 • Employment (Retired vs. not retired)
302 • Duration of Diabetes
303 • Hypoglycemia Unawareness
304 • MoCA total score
305 • WAIS-IV Processing Speed Index
306 • Functional activities questionnaire
307 • Frailty
308 • Prior CGM experience
309 • Prior Insulin Delivery Method
310 • C-peptide

311 **14. Exploratory Analyses**

312 All of the primary and secondary outcomes will be compared between PLGS and HCL in an
313 exploratory analysis that parallels the analysis described above. A difference, if any, in the
314 hypoglycemia outcomes between PLGS and HCL is expected to be small, so the power will be
315 low.

316 **15. Additional Tabulations and Analysis**

317 **15.1. Device use**

318 The percent of time in each system control mode and the percent of time using CGM will be

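### The zero-event fallback for severe hypoglycemia and DKA applies Barnard's test to event counts, although the test needs one yes/no result per participant

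*SAP*

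**What the plan says.** SAP 9 sets a threshold and a model for SH: "If there are at least 5 SH events across treatment arms, the SH incidence rate will be compared" "pairwise between all treatment arms using a repeated measures Poisson regression model", adjusted for period and for an event in the year before the study. If an arm is empty, the SAP says the model will not converge, "so the number of events will be compared pairwise using Barnard's test instead". DKA gets a similar analysis under the same five-event threshold. Protocol 11.8 carries the same fallback ("number of events will be compared pairwise using Barnard's test instead"), with the looser condition that there be enough events to analyze.

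Three other places bear on it:
- SAP 1: "Eligible participants will receive all three interventions and the order" in which they receive them is randomized, so the arms contain the same people.
- Protocol 9.4.1 lists among its grounds for stopping device use "Greater than two distinct severe hypoglycemia events as defined in section 9.1.2.1" and "Two distinct episodes of DKA (as defined in section 9.1.2) unrelated to infusion set" failure. Repeat events in one participant are therefore foreseen.
- SAP 11 includes a baseline item that is a count: "Participant reported number of SH and DKA 12 months prior to the start of the study".

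No section converts events into participants with an event, or states the denominator of the two-by-two table.

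**The concern.** Barnard's test compares two proportions. Each unit is in the table once, with or without an event. A total that includes repeats is not a number of people out of n, so the p-value is not valid once anyone has more than one event. The model being replaced is a model of rates and copes with repeats. The fallback loses that feature when the data are sparsest.

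SH and DKA are key safety outcomes in the protocol summary, and SAP 16.2 makes no multiplicity adjustment for safety. At stake is a single reported p-value below 0.05 that rests on two or three people.

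**Working it through.** **Inputs.** The documents attach no p-value or power to the fallback. The arm size comes from SAP 4: 84 participants, raised to 90 for 5% loss. That figure reproduces. With a standard deviation of 2.24 and correlation 0.3, the SD of a paired difference is 2.24 × √(2 × 0.7) = 2.65. The effect is 0.33 × 3.14 = 1.036. A paired t-test at two-sided alpha 0.025 and 90% power then needs 84. Dividing, 84/0.95 = 88.4, so 89 against the stated 90.

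**Step 1: one data set, two units.** Two-sided Barnard's test on k/90 against 0/90:

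| k against 0 | Barnard p |
|---|---|
| 2 | 0.210 |
| 3 | 0.094 |
| 4 | 0.045 |
| 5 | 0.025 |
| 6 | 0.014 |

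Five events against none give 0.025 on the literal reading, whoever had them (0.026 with 85 per arm). If three participants had the five events, the participant count is 3 against 0 and p = 0.094. If two had them, p = 0.21. The unspecified unit alone moves the result across 0.05.

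**Step 2: error rate when the fallback is reached.** Assume no treatment effect, so that each affected person's first event falls in any arm with chance 1/3. A second event falls in the same arm with an assumed chance q; q = 1/3 means events fall independently. The table gives the chance that some arm is empty and a given pair has p < 0.05, counting events, by full enumeration. Each pattern lists the number of events per affected person.

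| Pattern | q = 1/3 | q = 0.5 | q = 0.75 | q = 1 |
|---|---|---|---|---|
| 2,1,1,1 | 0.049 | 0.062 | 0.080 | 0.099 |
| 2,2,1 | 0.049 | 0.074 | 0.111 | 0.148 |
| 2,2,2 | 0.060 | 0.093 | 0.167 | 0.296 |
| 2,2,2,2 | 0.052 | 0.083 | 0.155 | 0.272 |
| 2,2,2,2,2 | 0.029 | 0.051 | 0.107 | 0.214 |
| 2,2,1,1,1,1 | 0.052 | 0.066 | 0.090 | 0.118 |

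One cell can be checked by hand. For 2,2,2 at q = 1 each of three people picks one arm. The pair A, B rejects if all three pick A (1/27), if two pick A and one picks C (3/27), or the same with A and B exchanged: 8/27 = 0.296.

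With no repeats (5, 6 or 8 single events) the chance is 0.049, 0.060 and 0.052. So there is no material inflation without repeats, nor when repeats fall independently.

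**Step 3: the same patterns counted by participant.** Barnard's test on participants with at least one event gives 0.000-0.060 across all nine patterns and every q. Exact McNemar on the same people gives 0.000-0.011. Its smallest p-value with d discordant participants is 2 × 0.5^d: 0.0625 for 5 and 0.031 for 6.

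**Step 4: how often the fallback is used.** Take three independent Poisson counts with equal means. The chance of at least 5 events in total and an empty arm is 0.006, 0.057, 0.148 and 0.049 at 0.5, 1, 2 and 4 events per period. The value 4 is an assumption: the 18% yearly figure in Protocol 1.1.1 gives 90 × (1 − 0.82^(12/52)) = 4.03, which counts people in a registry. No DKA rate is given. If one affected person in four is assumed to have a second event, simulation (200,000 runs) puts the per-pair chance of using the fallback and finding p < 0.05, at 1 to 4 events per period, at 0.01-0.03 for q = 1/3 and 0.03-0.065 for q = 1.

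**The case against.** **The wording may be shorthand.** Barnard's test presupposes a table of units with and without an event, so the plan may already mean participants. That is possible. But SAP 9 lists the number of SH events as an outcome in its own right, so the literal reading is natural, and a programmer would still need a denominator. The fix is the same either way.

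**Reach is small and the inputs are assumed.** This stands. The documents give no repeat rate and no measure of clustering. Protocol 9.4.1 shows that repeats are allowed for, not that they are expected. The upper figure of 0.30 needs every affected person to repeat, always in the same arm. Event counts, rates and a full listing are also reported, so a reader could see clustering in a few people.

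**A stronger reading: ignoring the crossover pairing also inflates error.** A reader might infer this because the same people are in every arm. The calculations do not support it. Barnard's test by participant, still unpaired, stays at 0.000-0.060 on every pattern. At 5 against 0 with five different people, the gap between 0.025 unpaired and 0.0625 paired mainly reflects how coarse exact McNemar is with so few discordant participants. It is not evidence of excess false positives.

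**Conclusion.** The rule is wrong as written, because event counts that include repeats do not fit the test it names. Severity is minor. The clearest effect is on a single reported p-value: 5 against 0 is 0.025 by event, but 0.094 or 0.21 by participant if three or two people had the events. These figures assume 90 observed per arm.

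A reader might also infer a serious long-run loss of error control. The documents do not support that: it would require repeats that cluster within a period, and they give no rate for either. Under the assumed patterns the per-pair chance is about 0.03-0.06 if events fall independently and 0.10-0.30 only at the extreme of q = 1. The SAP fallback is used only with at least 5 events in total and an empty arm. The primary endpoint and the hierarchical hypoglycemia endpoints do not use it.

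**What to change.** In SAP 9 replace "so the number of events will be compared pairwise using Barnard's test instead", and in Protocol 11.8 replace "number of events will be compared pairwise using Barnard's test instead", with wording to this effect: *for each pair of arms, Barnard's test will be applied to the number of participants with at least one event, out of the participants who started that treatment period.* Report the number of participants with events beside the event counts and the rates per 100 person-years.

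This changes wording in two documents and needs no new data. The cost is that p-values become less extreme when events repeat. The test can still reach p < 0.05 at 4 participants against 0 (0.045). It still ignores the pairing, but no inflation from that was found.

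A paired exact analysis (exact McNemar, or a within-participant label swap that keeps event counts) may be added as supportive. Exact McNemar should not be the default: it cannot reach p < 0.05 with fewer than 6 discordant participants, so it could not signal at the SAP's own threshold of 5 events.

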- 313 6) Most recent GFR \geq 30 ml/min/m² from local lab within the past 6 months
- 314 7) Willingness to use a rapid acting insulin compatible with the Tandem t:slim X2 pump
(currently aspart and lispro; other rapid acting insulins likely to be approved for pump use
prior to study initiation such as Fiasp)
- 317 8) Familiarity with and willingness to use a carbohydrate ratio for meal boluses
- 318 9) Willing to use study devices and automated insulin delivery features
- 319 10) Ability to download study devices at home or if not able to download at home willing to
320 come into clinic to bring devices for download of data at visits and as needed for safety
- 321 11) Participant is independently managing his/her diabetes with respect to insulin administration
322 and glucose monitoring (*may include assistance from spouse or other caregiver*)
- 323 12) Participant understands the study protocol, agrees to comply with it and is able to
324 successfully pass the consent understanding assessment with no more than 2 attempts.
- 325 13) Participant comprehends written and spoken English
- 326 14) At least 240 hours of CGM readings available during the end of run-in assessment
- 327 15) At least 1.5% of time with CGM glucose levels $<$ 70 mg/dL prior to SAP initiation
- 328 16) Active prescription for glucagon and willing and able to have glucagon available

329 **2.3 Participant Exclusion Criteria**

330 Individuals meeting any of the following exclusion criteria at baseline will be excluded from
331 study participation.

- 332 1) Use of PLGS technology or HCL insulin delivery in the past 1 month
- 333 2) History of 1 or more Diabetic Ketoacidosis episodes in the previous 6 months

334 3) Clinical diagnosis by a primary care provider, neurologist or psychiatrist of dementia, in the
335 investigator's opinion a suspected severe cognitive impairment such that it would preclude
336 ability to understand the study or use devices, or a score of 6 or less out of 15 on the 5 min
337 MoCA (5-min T MoCA Version 2.1) (mild cognitive impairment is not an exclusion)

338 4) A condition, which in the opinion of the investigator or designee, would put the participant or
339 study at risk, including severe vision or hearing impairment and any contraindication to the
340 use of any of the study devices per FDA labeling

341 5) Known adhesive allergy or skin reaction during the run-in pre-randomization phase or previous

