 83 CGM data prior to randomization will be used in the calculation of baseline CGM metrics. If
 84 <24hr of CGM data are available for any reason (e.g., lost data or device failure), then the
 85 baseline metrics will not be calculated and will be set to missing.

86 Follow-up

87 The first 4 weeks of CGM data in each period will be excluded to reduce the chance of a
 88 carryover effect since there is no washout period. Therefore, CGM metrics will be calculated for
 89 each period by pooling all sensor readings between midnight on the date of the treatment
 90 initiation visit + 29 days and midnight on the date of the end of treatment visit. If a participant
 91 drops out before completing the period, all data between midnight on the date of the treatment
 92 initiation visit + 29 days and midnight on the dropout date will be included. A minimum of 168
 93 hours of CGM data will be required to calculate CGM metrics.

94 Hypoglycemic Events

95 A CGM-measured hypoglycemic event will be defined as at least 2 sensor values <54 mg/dL that
 96 are 15 or more minutes apart plus no intervening values >54 mg/dL; at least 2 sensor values >70
 97 mg/dL that are 15 or more minutes apart with no intervening values <70 mg/dL are required to
 98 define the end of an event, at which point the study participant becomes eligible for a new event.

99 Daytime vs. Nighttime

100 Each of the CGM metrics listed will be calculated over 24 hours and separately for daytime
 101 (6am-<12am) and nighttime (12am-<6am). Daytime and nighttime versions of CGM % time <70
 102 mg/dL will be considered secondary. Minimum 126 hours of CGM data will be required to
 103 calculate daytime metrics and minimum 42 hours of CGM data will be required to calculate
 104 nighttime metrics.

105 **5.2. HbA1c**

106 The analysis windows for HbA1c at each time point are given in the table below:

Visit	Target Date	Window
Baseline	Randomization date	Screening visit date to randomization date +7 days
End of period 1	Period start date + 84 days	±21 days from target date. Values collected >7 days after the start of period 2 will be excluded.

End of period 2	Period start date + 84 days	±21 days from target date. Values collected >7 days after the start of period 3 will be excluded.
End of period 3	Period start date + 84 days	±21 days from target date. Values collected >7 days after the start of the extension period will be excluded.

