171 covariance will be fit including data from baseline and all three treatment periods. The model
172 will adjust for period as a covariate. It is expected that % time < 70 mg/dL will have a skewed
173 distribution. Therefore, values will be winsorized at the 10th and 90th percentiles. If winsorization
174 is not sufficient, other transformations will be explored.

175 There will be no imputation of missing data in the primary analysis. Missing data will be handled
176 by using a direct likelihood approach which will allow participants to be included even if they
177 only have baseline and no follow-up data.

178 **8. Analysis of the Secondary Endpoints**

179 **8.1. Secondary Hypoglycemia CGM Endpoints**

180 Summary statistics appropriate to the distribution will be given by treatment group for the
181 secondary hypoglycemia CGM endpoints (time <54 mg/dL and rate of hypoglycemic events).
182 The primary hypoglycemia endpoint and the secondary hypoglycemia outcomes will be
183 evaluated in a hierarchical approach to control the type 1 error (see section 16 below for details).
184 If the endpoint is to be formally compared between treatment groups, analysis will parallel that
185 of the primary outcome. It is also expected that time <54 mg/dL and rate of hypoglycemic events
186 will have a skewed distribution. Therefore, values will be winsorized at the 10th and 90th
187 percentile. If winsorization is not sufficient, other transformations will be explored.

188 Separate day and night versions of all three hypoglycemia CGM endpoints will be summarized
189 by treatment group but will only be formally compared between groups in a secondary analysis if
190 the overall version of the endpoint was formally compared and was statistically significant.

191 **8.2. Additional CGM Endpoints**

192 Summary statistics appropriate to the distribution will be given by treatment group for time in
193 range 70-180 mg/dL, mean glucose, time >180mg/dL, and time >250 mg/dL. These metrics will
194 be evaluated overall and separately for daytime and nighttime. Analysis will parallel the analysis
195 of the primary endpoint above. The outcomes will be winsorized at the 10th and 90th percentile if
196 they appear to be skewed. If winsorization is not sufficient, other transformations will be
197 explored.

198 **8.3. HbA1c**

199 HbA1c will be measured by central lab at baseline and following each 12 week period. Summary

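### Is the subgroup interaction for baseline time below 70 mg/dL biased because the same value is also a response in the primary model?

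*SAP*

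**What the plan says.** Here "SAP" means the statistical analysis plan; the sensor-augmented pump arm is called the control.

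SAP section 7 specifies a repeated measures model whose unstructured "covariance will be fit including data from baseline and all three treatment periods". Participants stay in the model even if they "only have baseline and no follow-up data", so baseline is a response row and not a covariate. Because skewness is expected, "values will be winsorized at the 10th and 90th percentiles". The model also adjusts for period.

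SAP section 13 lists "Baseline % time <70 mg/dL" among 15 factors. The sentence on method begins "The general approach for these exploratory analyses will be to add an" and continues "interaction term for the subgroup factor by treatment into the models used for the primary" analyses. It gives cut-points for education and employment only. Nothing says whether the baseline row takes a treatment level, whether it has its own factor effect, or whether this factor is continuous or split. Protocol section 11.12 is equally silent.

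Under SAP section 5.1, the last 14 days of "CGM data prior to randomization will be used in the calculation of baseline CGM metrics". Protocol section 3.4 has the run-in pump supplied with its suspend feature switched off, as in the control period (Protocol section 4.1).

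**The concern.** One measurement has two roles: it is a response in the baseline row and it defines the modifier. Run-in therapy resembles the control period, so a programmer could give the baseline row the control level. A single factor effect would then describe the high-minus-low gap both at baseline and in the control period. At baseline that gap is large because the groups are defined by it. In a later period it has shrunk by regression to the mean. The active periods carry only the shrunken gap, so both active arms would appear to help high-baseline participants more.

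That is the clinical question readers would ask of this factor. Entry requires "At least 1.5% of time with CGM glucose levels" below 70 mg/dL so that every participant has room to improve. A false signal would also enter the subgroup family for false discovery rate control in SAP section 16.2.

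**Working it through.** **Inputs.** From SAP section 4: SD 2.24, control mean 3.14, a 33% reduction, planning correlation 0.3 (0.5 also tabulated), about 0.8 seen in an earlier crossover, and 90 participants. The documents give no baseline-to-period correlation. I assume it equals the between-period correlation and show 0.3, 0.5 and 0.8.

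**The plan's own figure.** The effect is 0.33 × 3.14 = 1.036 points. The SD of a paired difference is 2.24 × √(2 × 0.7) = 2.65. With two-sided alpha 0.025 and 90% power, the normal approximation gives (2.241 + 1.282)² × 2.65² / 1.036² ≈ 81.2, so 82. Noncentral t gives 84, as stated.

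**Mechanism.** For normal data split at the median, the baseline gap is 2 × 2.24 × √(2/π) = 3.57 points. In a later control period it should be correlation × 3.57, which is 1.07, 1.79 and 2.86. With baseline coded as control, the fitted reference gap was 2.92, 3.16 and 3.39. With baseline as its own level it was 1.06, 1.75 and 2.88.

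**Simulation with no true interaction.** Constant effect of -1.036 in both active arms, six sequences of 15, normal data, not winsorized, median split. Entries are HCL/PLGS versus control in points, then rejection at nominal 5%.

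| Correlation | Baseline coded as control | Baseline as own level | Baseline row left out |
|---|---|---|---|
| 0.3 | -1.49/-1.47; 86% | +0.01/0.00; 6-8% | 0.00/-0.02; 6-7% |
| 0.5 | -1.01/-1.04; 69-72% | +0.02/+0.02; 5-6% | +0.02/0.00; 5% |
| 0.8 | -0.36/-0.36; 29-30% | -0.03/-0.02; 5% | -0.01/-0.01; 5-6% |

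With outcomes winsorized as in SAP section 7, control coding gives -1.42, -0.97 and -0.34 for PLGS (rejection 94%, 79%, 35%). Own-level coding stays within 0.05 of zero (3-7%). Applying the 1.5% entry criterion to a separate earlier value does not remove the bias (-1.45, -1.03, -0.41). Lognormal data with the same mean and SD, without that criterion, give -0.98, -0.59 and -0.17 (85%, 59%, 19%).

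**Other results.** With baseline as its own period level, the primary effects under control coding are -1.04/-1.04 against a true -1.036. A different factor with the same 1-point gap at baseline and in every period shows +0.03/0.00. If its 1-point gap fades to zero after run-in, control coding gives -0.47/-0.49 (19%) and own-level coding +0.01/+0.05 (6-7%). The mechanism is therefore not confined to one factor.

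**Would prescribing a three-period model help?** Take a proportional 33% reduction with lognormal data. The true interaction for a median split is -0.33 × 2 × 3.14 × (2Φ(r·s) - 1), where s² = ln(1 + (2.24/3.14)²) = 0.411 and r is the correlation on the log scale (0.345, 0.551, 0.830). This gives -0.36, -0.57 and -0.84.

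| Correlation | True | Three periods, winsorized | Control coding, winsorized |
|---|---|---|---|
| 0.3 | -0.36 | -0.10 | -0.95 |
| 0.5 | -0.57 | -0.16 | -0.77 |
| 0.8 | -0.84 | -0.29 | -0.61 |

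The three-period model recovers 28%, 28% and 35% of the true value. At 0.5 and 0.8 it is further from the truth (errors 0.41 and 0.55) than control coding (0.20 and 0.23). With lognormal data, a constant effect, a continuous factor and correlation 0.8, it rejects falsely in 27-30% of trials against 15-20% under control coding. Winsorizing drives these distortions, and recoding the baseline row does not address that.

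**Which coding the text supports.** SAP section 7 names baseline and the treatment periods as separate things. SAP section 8.4 summarizes questionnaires by treatment group and, separately, at baseline. SAP sections 15.2, 15.4 and 15.5 tabulate baseline alongside the arms and not within the control. No section assigns baseline to the control arm.

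**The case for a change.** The strongest case for acting is that the plan is silent, the run-in regimen makes control coding a natural choice, and one sentence would settle it. At the planning correlation of 0.3, the artefact of 1.4 to 1.5 points exceeds the 1.04-point effect that the trial is sized to detect. False discovery rate control does not remove bias, and a spuriously small p-value can loosen the threshold for the other subgroup tests.

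Most of this stands as a conditional statement: the silence is real, and control coding would mislead. Three things weaken it. The harm needs a coding that the SAP never states and that fits poorly with how it handles baseline elsewhere. The highest rejection rates come from normal data, which at mean 3.14 and SD 2.24 put about 8% of values below zero, and from an effect constant in points. The plan thinks in relative reductions, under which a real interaction in the same direction exists. Finally, a three-period model matches own-level coding where the latter is used, and it is not reliably better than control coding on the skewed, winsorized data that the SAP expects.

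**Conclusion.** No change follows. The SAP leaves a coding detail open, and the ordinary choice, a pre-treatment row with its own level and factor effect, gives interactions within 0.05 points of zero when none exists. Some versions of the problem would also show themselves: if a continuous factor and the baseline response are the same number (both raw or both winsorized), the baseline residual variance collapses to zero.

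If the row were coded as control, the false interaction would run from about -1.4 points at correlation 0.3 to about -0.35 at 0.8, and that result should not be believed. These figures assume 90 participants, equal SDs, no missing data, a constant effect, normal data, a median split and a baseline correlation equal to the between-period one.

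What is exposed is one of 15 factors, or a few if other associations fade after run-in, in analyses that the SAP labels exploratory. The primary comparisons, their error control and the sample size do not depend on it.
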